3. INTERIM ANALYSIS AND, DATA MONITORING COMMITTEE REVIEW

An interim analysis (IA) is planned when approximately 60% of the initial planned 110 participants have completed the Week 12 visit and approximately 30% of participants have completed the Week 24 visit to re-estimate the sample size to ensure adequate power for the hypothesis testing. All cumulative data will be used for the interim analysis. Details for the sample size re-estimation (SSR), threshold for the conditional power, and protection of overall significance level will be provided in DRC charter for the IA and monitoring. The planned maximum total sample size after SSR is 150 participants. IA contents will be defined in DPS.

The Data Monitoring Committee (DMC) is not applicable. Instead, a data review committee (DRC) is used for the interim analysis. Details are included in the DRC charter.

4. SUBJECT INFORMATION

The number of subjects in each analysis set will be summarized and listed by treatment group, and overall. In addition, the distribution of subjects by site ID will be presented unless otherwise noted.

4.1. Demographics and Baseline Characteristics

Table 3 presents a list of the demographic variables that will be summarized by treatment group, and overall for the ITT, safety, and PP analysis sets. Additionally, baseline disease characteristics data are listed in Table 4. Demographics and baseline disease characteristics will also be summarized and analyzed by study subgroups listed in Section 2.5 using the ITT analysis set.

Table 3: Demographic Variables

Continuous Variables:	Summary Type
Age (years)	
Weight (kg)/(pounds)	
Percent weight gained on current INI+TAF/FTC regimen at screening	D
Duration of virologic suppression on current INI+TAF/FTC regimen	Descriptive statistics (N, mean,
(month)	standard deviation [SD], median
Duration of infection (month)	and range [minimum and
Height (cm)	maximum])
Body Mass Index (BMI) (kg/m²)	1
Waist circumference (cm)	1
Categorical Variables	
Age (18-25 years, 26-50 years, 51-64 years, and ≥65 years)	
Baseline history of hypertension (yes/no)	†
Baseline history of diabetes (yes/no)	†
Baseline history of dyslipidemia (yes/no)	†
Baseline active neurologic comorbidities (yes/no)	†
Baseline active psychiatric comorbidities (yes/no)	†
Number of active neurologic/psychiatric comorbidity (1, 2, 3, 4, >/=5)	
Baseline HbA1c > 6.5% (yes/no)	
Antihypertensives, antihyperglycemic agents or lipid lowering agents	
(yes/no)	
Sex (male, female)	
Gender (male, female, male-to-female, female-to-male, non-binary/other)	†
Race (Black/African American, Non-Black/African American)	†
Race:Sex (Black/African American Female, Black/African American	†
Male, Non-Black/African American Female, Non-Black/African American	
Male)	Frequency distribution with the
Race ^a (Black/African American, White, American Indian or Alaska	number and percentage of subjects
Native, Asian, Native Hawaiian or other Pacific Islander, Other, Unknown,	in each category.
Not reported)	
Ethnicity (Hispanic or Latino, not Hispanic or Latino, Unknown, Not	
reported)	
BMI (normal 18-<25 kg/m2, overweight 25-<30 kg/m2, obese ≥30 kg/m2)	
Woman of childbearing potential (Of childbearing potential/Permanently	
Sterilized/ Postmenopausal/ NA)	
Nicotine use (Never used, current user, former user)	
Alcohol consumption (Never used, current user, former user)	
Drug Use (Never used, current user, former user)	
Highest education level (Less than high school,)	
Marital status (Single- newer married, married,)	
Employment status (Employed full time for wages,)	
State belongs to (Alabama,)	
Social support of the subject (Friend, Family member,)	
Current housing situation	
If multiple race enterprise are indicated, the Pace is recorded as 'Multiple'	

^a If multiple race categories are indicated, the Race is recorded as 'Multiple'

Table 4: Baseline HIV disease characteristics

Continuous Variables:	Summary Type
Baseline CD4+ (absolute count and %)	Description statistics (NI mann
Baseline-screening eGFRcr ^a	Descriptive statistics (N, mean,
Baseline HIV-1 viral load (absolute count)	standard deviation [SD], median

Approved, Date: 24 March 2023

Duration of INI + TAF/FTC treatment at baseline (years)	and range [minimum and
Duration of TAF use (years)	maximum]).
Duration of ART (years)	
Categorical Variables:	
Type of INI regimen at baseline	
Number of previous ART regimens	
Switched previous regimens for AE, VF, Convenience and Other	
HIV Acquisition Risk Factor (Heterosexual contact, MSMs, Others ^b)	
Baseline viral load ($<50, \ge 50 \text{ HIV-1 RNA copies/mL}$)	
Baseline CD4 cell count (\(\leq 200\), 200\(\leq x \leq 350\), 350\(\leq x \leq 500\), >500)	
cells/mm3)	
HIV-1 subtype (B, Non-B)	
Historical evidence of DRV RAM	
• yes/no	
• V11I	
• V32I	
• etc.	Frequency distribution with the
Historical evidence of FTC RAM	number and percentage of subjects
• yes/no	in each category.
• K65R	
• K65E	
• etc.	
Historical Evidence of TFV RAM	
• yes/no	
• K65N	
• K70E	
• etc.	
Historical Evidence of INI RAM	
• yes/no	
• T66A	
• T66I	
• etc.	
	1 XX : 1 (TDXX) (1 (1 : 1) A 1:

^a If a participant's actual body weight is greater than 20% over their Ideal Body Weight (IBW), the participant's Adjusted Body Weight (ABW) will be used for eGFRcr (Cockcroft-Gault Formula). IBW(male) = 50kg + 0.9kg x (height(cm) – 152). IBW (female) = 45.5kg + 0.9kg x (height(cm) – 152. ABW= IBW(kg) + 0.4 x (Weight(kg) – IBW(kg)).

4.2. Disposition Information

A tabulation of the total number (with percentages) of subjects screened (and reason for screen failures), randomized and not treated, and randomized and treated will be provided.

Tabulation per treatment arm and overall of the number of subjects who have completed the treatment phase, who are ongoing, and who have discontinued the trial before Week 48 visit, with the reason for discontinuation will be provided.

A Kaplan-Meier graph for the time to Discontinuation (any reason) will be included.

The number of subjects in the following disposition categories will be summarized throughout the study:

• Subjects receiving study intervention

^bOthers=Intravenously injectable drug use, Blood transfusion, Hemophilia-associated injections, Occupational exposure, Mother to child transmission, and Other

- Subjects completing the study
- Subjects who discontinued study intervention
- Reasons for discontinuation of study intervention

The above categories will include summaries. A listing of subjects will be provided for the following categories:

• Subjects who discontinued study intervention

4.3. Treatment Compliance (Adherence)

Treatment adherence defined based on participant self-report using a 4-day recall as collected Drug Adherence page of eCRF for the study will be assessed at all study visits by participant self-report using a 4-day recall.

Adherence rates will be reported according to the proportion of participants missing 0, 1, 2, 3 or 4 doses using participant self-report 4-day recall at Weeks 4, 12, 24, 36, and 48.

4.4. Extent of Exposure

The number and percentage of subjects who receive study drug of both D/C/F/TAF FDC arm and active-control arm will be summarized by treatment group.

Descriptive statistics, (N, mean, SD, median, and range (minimum, maximum)), will be tabulated for the duration of treatment of both D/C/F/TAF and control, in weeks, during the respective active treatment phases, up to the Week 48 visit, or in case of early discontinuation, last study medication intake for the ITT analysis set. In addition,

- subject-years of exposure will be shown, derived as mean of treatment duration ((in weeks) x N) x 7 / 365.25...
- subject-weeks of exposure are calculated as (days of exposure)/7. Subject-weeks will be presented.
- treatment duration (in weeks) is defined as follows for each of the two treatment arms:

(End of phase - start of phase + 1) / 7

Treatment interruptions will not be taken into account for the above definition.

• total dose days of exposure is defined as the total number of days that study intervention was administered to the subject (excluding days of known study treatment interruption). If dates of study treatment interruptions are not fully known, in terms of start and end date of interruption, these interruptions will not be excluded from total days of exposure.

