Screening	Minimum of date of signing the informed consent and date of the screening visit, no early than Day -42	1 day before start of treatment or day 1 of treatment whichever the last before first dose.
Treatment	Date of the first intake (after	For ongoing/completed subjects, in order of priority:
Phase I	randomization)	 For delayed switched arm, use first D/C/F/TAF intake date – 1;
		- For immediate switch arm, use Week 24 visit date; if missing then
		 Projected Week 24 visit date
		Projected Week 24 visit date = first dose date $+ (7 \times 24)$.
		In case of withdrawal before Week 24 visit : Date of last intake +7 days. If the last dose date is missing, use the following date in order of priority:
		- The date of treatment termination + 7 days;
		- The first available follow-up visit date-1 day;
		- The earlier of projected Week 24 visit date +7 and Trial discontinuation date + 7, where projected Week 24 visit date = first dose date + (7×24).
Treatment	Treatment Phase I end date +1	For ongoing/completed subjects, in order of priority:
Phase II	day	- Week 48 visit date + 7; if missing then
		 Projected Week 48 visit date +7, where projected Week 48 visit date = first dose date + (7×48).
		In case of withdrawal after Week 24 visit: Date of last intake +7 days. If the last intake date is missing, use the following date in order of priority:
		- The date of withdrawal + 7 days;
		- The first available follow-up visit date-1 day;
		- The earlier of projected Week 48 visit date +7 and trial discontinuation date + 7, where projected Week 48 visit date = first dose date + (7×48).
*Follow-up	End of the last treatment phase +1 day	Trial termination date for all groups (date of last contact)

⁺¹ day contact)

*30 day follow-up visit required for any subject who has ongoing AE or SAE at the time of his last study visit.

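### The treatment-duration formula in SAP 4.4 relies on phase end dates that run 7 days past the end point the same section gives, so treatment duration and subject-years are overstated if it is followed literally

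*SAP*

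**What the plan says.** SAP 4.4 (Extent of Exposure) opens by setting the period over which duration is summarised: "up to the Week 48 visit, or in case of early discontinuation, last study medication intake for the ITT analysis set". It then defines treatment duration in weeks, for each arm, as ("End of phase - start of phase + 1) / 7". Subject-years use the same quantity and are "derived as mean of treatment duration ((in weeks) x N) x 7 / 365.25". The section gives no phase dates of its own.

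The only phase dates are in the trial-phase table of SAP 2.2 (Visit Windows):

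- **Phase II, ongoing or completed:** "Week 48 visit date + 7; if missing then" the fallback, "Projected Week 48 visit date +7, where projected Week 48 visit date = first dose date + (7×48").
- **Phase II, withdrawal:** "In case of withdrawal after Week 24 visit: Date of last intake +7 days".
- **Phase I, withdrawal before Week 24:** "Date of last intake +7 days. If the last dose date is missing, use the following date in order of priority".
- **Phase I, Immediate Switch participants who pass Week 24:** "For immediate switch arm, use Week 24 visit date; if missing then" a projected Week 24 date. No 7 days are added.
- **Phase I, Delayed Switch participants who pass Week 24:** the day before the first D/C/F/TAF intake. Again no 7 days are added.

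SAP 2.2 introduces these phases for three uses: adverse events, concomitant therapies and worst-case cross-tabulations. Exposure is not among them. The 7-day tail matches the treatment-emergent window in SAP 7.1.2. The SAP amendment history records that the treatment phase end was moved to 7 days after the visit for ongoing and early-withdrawal subjects.

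**The concern.** Two statements in one section give different end dates. The opening sentence stops the clock at the Week 48 visit or the last intake. The formula stops it at the end of a phase that was built to catch late adverse events. A programmer who implements the formula with the phase dates in SAP 2.2 counts seven days beyond the section's own end point as time on treatment. Protocol 6.6 says D/C/F/TAF is not supplied after completion or discontinuation, so for that regimen the tail is not study treatment.

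The excess is also uneven. Everyone's last treatment phase carries the tail under the main rules, but Phase I carries it only for withdrawals before Week 24. Exposure to INI + TAF/FTC is therefore lengthened only for those withdrawals, while exposure to D/C/F/TAF is lengthened for nearly everyone who takes it. SAP 4.4 describes both regimens in the same summary, and they would not be counted alike.

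**Working it through.** The plan states no exposure figure, so there is none to reproduce. The check applies the SAP 4.4 formula twice: once with the end point in that section's opening sentence, and once with the SAP 2.2 phase end.

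**Inputs.** Day 1 is the first dose. Target days come from the visit-window table in SAP 2.2: Week 24 is Day 24×7+1 = 169 and Week 48 is Day 48×7+1 = 337. There are 55 participants per arm (SAP 2.1). The maximum total after re-estimation is 150, or 75 per arm (SAP 1.5).

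**Assumptions.** Visits fall on target days, the Delayed Switch arm first takes D/C/F/TAF on Day 169, and the subject-years figures assume no dropout.

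**Formula.** Weeks = (end − start + 1)/7.

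| Case | Start | End per 4.4 text | Weeks | End per 2.2 phase | Weeks | Excess |
|---|---|---|---|---|---|---|
| Immediate, Phases I+II, completer | 1 | 337 | 337/7 = 48.14 | 344 | 344/7 = 49.14 | 2.1% |
| Immediate, Phase II, completer | 170 | 337 | 168/7 = 24.00 | 344 | 175/7 = 25.00 | 4.2% |
| Delayed, Phase II, completer | 169 | 337 | 169/7 = 24.14 | 344 | 176/7 = 25.14 | 4.1% |
| Immediate, Phase I, passes Week 24 | 1 | 169 | 24.14 | 169 | 24.14 | 0 |
| Delayed, Phase I, passes Week 24 | 1 | 168 | 24.00 | 168 | 24.00 | 0 |
| Last dose Day 28 | 1 | 28 | 4 | 35 | 5 | 25.0% |
| Last dose Day 84 | 1 | 84 | 12 | 91 | 13 | 8.3% |
| Last dose Day 140 | 1 | 140 | 20 | 147 | 21 | 5.0% |
| Last dose Day 252, both phases | 1 | 252 | 36 | 259 | 37 | 2.8% |

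For the two Phase I rows of participants who pass Week 24, the column for the 4.4 text shows the SAP 2.2 phase end, because the 4.4 sentence gives no separate Week 24 end point. The excess is 7 days wherever the tail applies; only the base changes.

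**Subject-years**, as mean weeks × N × 7/365.25, with 55 completers per arm:

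- Immediate Switch: 55×337/365.25 = 50.75, against 55×344/365.25 = 51.80.
- Delayed Switch on D/C/F/TAF: 55×169/365.25 = 25.45, against 55×176/365.25 = 26.50.
- Excess: 55×7/365.25 = 1.05 subject-years per arm. With 75 per arm it is 75×7/365.25 = 1.44.

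**Ongoing participants.** SAP 1 and 1.3 say that data beyond Week 24 are also summarised at the primary analysis. A participant still on study then has no Week 48 visit, and the SAP 2.2 fallback is the projected Week 48 date plus 7 days. If Phase II exposure is tabulated at that point, the formula would credit time that has not yet elapsed. The SAP does not say whether exposure is among the data so summarised.

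**The case against.** The best reply is that SAP 4.4 already states the intended end date in its opening sentence, and that SAP 2.2 does not list exposure among the uses of the phases. A programmer could read the end of phase in the formula as the Week 48 visit or last intake and add nothing. That is a fair account of what was probably meant, and it means one cannot say that the final tables will be overstated. It does not remove the defect. The formula names a quantity that the SAP defines in one place only, and that definition carries the 7 days.

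Stronger readings are tempting, and the documents do not support them:

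- **That all exposure measures are wrong.** Total dose days are defined in SAP 4.4 from days actually administered and do not use phase dates. Subject-weeks use days of exposure and are affected only if those days are taken from the phases.
- **That the Delayed Switch arm is inflated more than the Immediate Switch arm.** This compares one 24-week phase with two phases combined. Phase II against Phase II, the excess is 4.1% and 4.2%.
- **That safety comparisons or the primary result are biased.** SAP 7.1.2 summarises adverse events as numbers and percentages of subjects, plans no formal testing and specifies no exposure-adjusted rates. The primary weight model in SAP 5.2.3 does not use exposure.

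The 25% and 8.3% figures describe single early stoppers. The documents give no expected share of such participants, so no arm-level effect follows from them. Not every fallback date adds 7 days either: the one based on the first follow-up visit subtracts a day from that visit.

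**Conclusion.** The point holds as a contradiction within SAP 4.4. The stated formula, applied with the only phase dates the SAP provides, gives a treatment duration 7 days longer than the section's own end point in each participant's last phase, and subject-years inherit the excess.

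For completers the effect is small, about 2% over 48 weeks or 4% over Phase II. It is larger in relative terms for early stoppers and falls mainly on D/C/F/TAF. These sizes rest on visits at target days and on the main end-date rules rather than the fallbacks. The consequence is confined to a descriptive exposure table. This is a minor correction, worth making because the table would otherwise disagree with its own definition.

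**What to change.** Add to SAP 4.4 that, for exposure:

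- the end date is the Week 48 visit for completers or the last intake for early discontinuations, without the 7 days and never beyond the data cut-off;
- start dates stay as in SAP 2.2, that is, first intake after randomization and, for the Delayed Switch arm's Phase II, first D/C/F/TAF intake;
- the end of Phase I for participants who pass Week 24 stays as in SAP 2.2;
- where the last intake is missing, the SAP 2.2 fallback dates apply with the 7 days removed.

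Keep the 7-day phase ends for adverse event assignment only.

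Replacing the formula by first to last intake within each regimen would not be a safe shortcut. Participants have taken INI + TAF/FTC for at least six months before screening (Protocol 5.1), so that wording could count pre-study time in the control regimen. It would also replace the Week 48 visit that the SAP already uses for completers.

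The cost is a short addition to one SAP section and the matching programming. The dates needed are already called for by SAP 2.2, so no new data are required.

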4.5. Protocol Deviations

In general, the following list of major protocol deviations may have the potential to impact subjects' rights, safety or well-being, or the integrity and/or result of the clinical study. Subjects with major protocol deviations will be identified prior to database lock and the subjects with major protocol deviations will be summarized by category.

• Developed withdrawal criteria but not withdrawn

- Entered but did not satisfy inclusion/exclusion criteria
- Received a disallowed concomitant treatment
- Received incorrect dose
- Other

4.6. Prior and Concomitant Medications

Prior and Concomitant medications will be coded using the World Health Organization Drug Dictionary (WHO-DD). Prior medications are defined as any therapy used before the Baseline Day 1. Concomitant medications are defined as any therapy used on or after the same day as the Baseline Day 1.

Summaries of concomitant medications will be presented by treatment group. The proportion of subjects who receive each concomitant medication and the proportion of subjects who receive at least one concomitant medication will be summarized.

Summaries of concomitant medications will be presented by ATC term. A summary of participants with changes in medications of interest at Week 48 will be reported.

Prior and concomitant therapies will be summarized and grouped as follows by treatment group for specific drugs, using a list of dictionary derived terms provided as metadata. These groups will be tabulated (n, %) per treatment group and analysis phase:

- lipid lowering drugs
- antidiabetic drugs
- antihypertensive drugs
- drugs for cardiovascular disease
- antiosteoporotic drugs
- antidepressants
- antipsychotics
- steroids
- thyroid medications

Prior medications will be summarized by ATC term.

4.7. Medical History

Subjects past and/or concomitant diseases will be tabulated by medical history categories, general medical history, and family history, separately by treatment group. Tabulation (n, %) will be done by body system and medical term. Additionally, all medical history will be listed by medical history category.

5. METABOLIC/WEIGHT

5.1. Analysis Specification

In general, continuous variables will be summarized using descriptive statistics including the number of participants, mean, standard deviation (SD), two-sided 95% confidence interval (CI), median, and range. Binary or categorical variables will be summarized using the number and percentage of participants in each category. Descriptive summaries will be provided by stratification factors (sex and race). Graphic displays will also be used to summarize the data.

5.2. Primary Endpoint

5.2.1. Definition

The primary endpoint is defined as the percent change in body weight at Week 24 from Baseline.

5.2.2. Primary Estimand

The main analysis of the primary endpoint will be conducted by using the following estimand attributes:

A) Study Intervention:

- o Arm 1: D/C/F/TAF FDC Arm (Immediate Switch)
- o Arm 2: Active-Control Arm (Delayed Switch)
- **B)** Study population: Type 1 (HIV-1) infection currently treated subjects with a stable ARV regimen consisting of an INI combined with TAF/FTC for ≥ 6 consecutive months preceding the screening visit and experiencing a $\geq 10\%$ increase in body weight within 12 months' time period
- C) Variable: Percent change in body weight at Week 24 from Baseline

D) Intercurrent events:

- Treatment discontinuation prior to Week 24: if the participant discontinued treatment prior to Week 24 but weight assessments are available at that time point, all data will be used regardless of occurrence of the intercurrent event (treatment policy strategy).
- Major protocol deviations: all data are used regardless of the occurrence of major protocol deviations (treatment policy strategy).
- Deaths prior to Week 24: participants who die prior to Week 24 will be included with the weight data available prior death.

E) Population-level summary: Mean difference in %weight change at Week 24 between study intervention arms.

5.2.3. Analysis Methods

The statistical hypothesis is the following:

 H_0 : Dt-Dc=0 versus H_1 : Dt -Dc \neq 0.

Where H₀ is the null hypothesis, H₁ is the alternative hypothesis; Dt= percent change in body weight at Week 24 from Baseline for D/C/F/TAFFDC (Immediate Switch Arm), Dc = percent change in body weight at Week 24 from Baseline for active control (Delayed Switch Arm).

The statistical hypothesis will be tested using mixed model for repeated measures (MMRM) below.

Y = Baseline BMI + Sex + Race + Time + Treatment + Treatment*Time + Subject + E

In this model, Y is the %change in body weight from baseline at time week 4, week 12, and week 24; baseline BMI, sex, race, time, treatment and treatment*time are fixed effects; subject is a random effect; and E is the random error. Subject is treated as a random effect to incorporate the variability and correlation among repeated measures (time).

The statistical hypothesis will be tested by estimating the treatment LSmeans for the %change in body weight corresponding to the time measurement at week 24. The significance level p-value and 95% confidence interval for the difference will be provided.

To control for the overall Type I error rate at the 2-sided 0.05 significance level, the weighted inverse-normal p-value combination test will be used to combine p-values from interim stage and primary analysis stage⁴. The overall p value will be calculated by the combination statistic below

$$Z(p_1,\,p_2) = \text{w1}\ \Phi^{-1}(1 - p_1) + \text{w2}\ \Phi^{-1}(1 - p_2)$$

where $w_1=\sqrt{(n_1/N)}$, $w_2=\sqrt{(n_2/N)}$, n_1 and n_2 are number of subjects in IA stage and remaining primary stage.

All available data from randomized participants that have received at least one dose is included (ITT analysis set) will be used for the analysis, regardless of the occurrence of intercurrent events.

Missing Data for body weight is assumed as Missing At Random (MAR). In addition, as a sensitivity analysis, a control-based multiple imputation will be applied to the MMRM model, assuming weight data is not missing at random.

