9.4.2. Primary Analysis

The primary endpoint analyses will be based on the ITT population. The analysis will be conducted using linear mixed-effects model with participant as random effect adjusted by baseline BMI and stratification factors in a longitudinal data with repeated measures (percent body weight change measured at multiple visits).⁴⁰

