9.4.3. Secondary Analyses

9.4.3.1. Metabolic Analyses

For the metabolic endpoints of change from baseline, the same statistical model as described for the primary endpoint will be used for analysis. All other endpoints will be analyzed using descriptive statistics.

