1.5. Sample Size Justification

[figure not shown]
Using a T-test with 80% power to detect a difference of 3% at the significance level of 0.05, 2-sided, the sample size per treatment arm is a simple function of effect size (ES): $n_{arm}=16/(ES)^2$. The effect size is the standardized difference: $ES=\Delta/\sigma$, where Δ is the difference between the two arms, and σ^2 is the common variance. Since there was no direct data on the study population to assume the observed difference, Δ =3% is considered a clinical meaningful difference. Internal data from 2 Phase 3 studies^{2, 3} on D/C/F/TAF FDC arm from different HIV patient populations (naive, switch) have shown the %body weight change in the range of 1.5% to 1.8% and standard deviation from 4.0 to 4.6 (Table 1 and Figure 2), resulting a range of ES and corresponding sample size³.

Table 2 Phase 3 Studies on D/C/F/TAF FDC Arm

Study	AMBER D/C/F/TAF arm	EMERALD D/C/F/TAF arm
N % body weight change from baseline at week 24 (SD)	347 1.5 (4.6)	738 1.8 (4.0)
N % body weight change from baseline at week 48 (SD)	340 2.3 (5.0)	728 1.9 (5.1)

(Data on file)

Figure 2: Sample Size Estimation by Treatment Effect Size

Given the uncertainty of either the Δ or the variability, an adaptive unblinded SSR is planned to reestimate the sample size in an IA to ensure adequate power in the hypothesis testing for the primary endpoint using the conditional power approach. An initial sample size of 55 participants per treatment arm (110 participants total) will be used for treatment effect size of 0.54 (ADDPLAN version 6). The IA is planned when approximately 60% of the initial planned 110 participants have completed the Week 12 visit and approximately 30% of participants have completed the Week 24 visit to re-estimate the sample size to ensure adequate power for the hypothesis testing. All cumulative data will be used for the IA. The planned maximum total sample size after SSR is 150 participants. Details for the SSR,

threshold for the conditional power, and protection of overall significance level will be provided in the statistical plan for the IA and monitoring.

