6.2. Secondary Endpoints and Analysis Methods

6.2.1. Weeks 24 and 48 Endpoints

In the following, the secondary endpoints at Week 24 are defined for D/C/F/TAF FDC regimen (Immediate Switch Arm) versus INI + TAF/FTC ARV regimen (Delayed Switch Arm), while the secondary endpoints at Week 48 are related to D/C/F/TAF FDC (Immediate Switch Arm) only.

Metabolic:

- Change from Baseline in absolute body weight over time
- Proportion of participants with % change from baseline in body weight >5% over time.
- Proportion of participants with % change from baseline in body weight >3% over time.
- Change from Baseline in BMI over time.
- Change from Baseline in body composition as measured by DEXA scan at Week 24 and Week 48, respectively.
- Change from Baseline in waist circumference over time.
- Change in SBP and DBP from Baseline over time.
- Change from Baseline in fasting lipids over time.
- Change from Baseline in fasting glucose over time.
- Change from Baseline in HOMA-IR at Week 24 and Week 48, respectively.
- Change from Baseline in HbA1c at Week 24 and Week 48, respectively.
- Change from Baseline in leptin and adiponectin at Week 24 and Week 48, respectively.
- Change from Baseline in the proportion of participants with advanced fibrosis according to the NAFLD fibrosis score at Week 24 and Week 48, respectively.
- Change from Baseline in the proportion of participants at high risk of NASH according to the HAIR score at Week 24 and Week 48, respectively.
- Proportion of participants having a dose-reduction or complete withdrawal of anti-hypertensive, anti- hyperglycemic, or lipid lowering agents in the Immediate Switch Arm from Baseline to Week 24 and Week 48, respectively or Delayed Switch Arm from Baseline to Week 24.
- Proportion of participants initiating an anti-hypertensive, anti-hyperglycemic, or lipid lowering agent in the Immediate Switch Arm from Baseline to Week 24 and Week 48, respectively or Delayed Switch Arm from Baseline to Week 24.

Safety:

- Incidence of any Grade AEs (related and not related) through Week 24 and Week 48, respectively.
- Incidence of Grade 3 and 4 AEs (related and not related) through Week 24 and Week 48,

- respectively.
- Incidence of discontinuations due to AEs through Week 24 and Week 48, respectively.
- Incidence of SAEs (related and not related) through Week 24 and Week 48, respectively.
- Change from Baseline in clinical laboratory tests over time.
- Incidence of Grade 3 and 4 laboratory abnormalities over time.

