6.2.2. Secondary Analysis Methods

6.2.2.1. Metabolic Analyses

Secondary metabolic endpoints will be analyzed using descriptive statistics and frequency tabulations.

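### Metabolic change endpoints are compared between arms without adjustment for their own baselines, and the protocol and SAP disagree on whether they are modelled at all

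*SAP*

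**What the plan says.** SAP 5.2.3 gives the primary model as "Y = Baseline BMI + Sex + Race + Time + Treatment + Treatment*Time + Subject + E", where "Y is the %change in body weight from baseline at time week 4, week 12, and week 24". Protocol 9.4.2 agrees: a "linear mixed-effects model with participant as random effect adjusted by baseline BMI and stratification factors". Neither has a term for baseline body weight.

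For the secondary endpoints the two documents part ways:

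- Protocol 9.4.3.1, and the statistical methods part of the synopsis: "For the metabolic endpoints of change from baseline, the same statistical model as described for the primary endpoint will be used for analysis". Nothing is said about replacing BMI with the endpoint's own baseline, or adding that baseline.
- SAP 6.2.2.1: "Secondary metabolic endpoints will be analyzed using descriptive statistics and frequency tabulations". No model is named.

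The Week 24 metabolic objectives in Protocol 3.1 and SAP 1.1.2.1 nonetheless remain comparisons of the Immediate Switch Arm with the Delayed Switch Arm. The Schedule of Activities (Protocol 1.3) collects a baseline for each of these measures.

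**The concern.** A change score is usually related to its own starting value: participants who start high by chance tend to fall, and those who start low tend to rise. Adjusting for that starting value removes this variation and corrects for chance imbalance between arms.

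Baseline BMI does this job poorly for blood pressure, lipids, glucose, HOMA-IR, HbA1c, leptin or adiponectin. If the protocol's text is followed, each of these is adjusted for BMI and not for itself. If the SAP's text is followed, raw mean changes are set side by side with no adjustment at all, so BMI, sex and race drop out as well.

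At stake are wider intervals than necessary for the secondary metabolic results, and between-arm contrasts that carry whatever baseline imbalance happens to arise with about 55 participants per arm.

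**Working it through.** **Inputs from the documents.** SAP 1.5: "Using a T-test with 80% power to detect a difference of 3% at the significance level of 0.05, 2-sided", effect size 0.54, 55 per arm, and a standard deviation (SD) of Week 24 percent weight change of 4.0 to 4.6 in two earlier studies. Allocation is 1:1 (SAP 1.6.1). Height is measured once, at screening, and used for BMI at every visit (SAP 7.3.2). The documents give no correlation between baseline and Week 24 for any endpoint, so the correlations below are assumptions shown as ranges.

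**The plan's own figure.** 16/0.54² = 54.9, so 55 per arm. A two-sample t-test with 55 per arm and effect size 0.54 has power 0.801. The figure reproduces. It takes no credit for any covariate, so the choice of covariates does not make it wrong.

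**Secondary change endpoints.** Let r be the baseline-to-Week-24 correlation. Assume equal variances σ² at both times, and that BMI, sex and race explain none of the change.

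- Variance of the raw change: 2σ²(1 − r).
- Residual variance after adjusting for own baseline: σ²(1 − r²).
- Ratio: (1 + r)/2.

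| r | variance ratio | standard error ratio | equivalent increase in participants (1/ratio − 1) |
|---|---|---|---|
| 0.5 | 0.75 | 0.866 | 33% |
| 0.6 | 0.80 | 0.894 | 25% |
| 0.7 | 0.85 | 0.922 | 18% |
| 0.8 | 0.90 | 0.949 | 11% |
| 0.9 | 0.95 | 0.975 | 5% |

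As an illustration only, since no secondary endpoint has a power target: an endpoint with 80% power unadjusted would have about 90%, 86% and 82% at r = 0.5, 0.7 and 0.9.

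**Chance imbalance.** With 55 per arm, the standard error of a baseline mean difference is √(2/55) = 0.19 SD. An imbalance of that size moves an unadjusted change contrast by (1 − r) × 0.19: about 0.10 SD at r = 0.5, 0.04 at r = 0.8 and 0.02 at r = 0.9.

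**Endpoints where little or nothing is gained.**

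- *Change in BMI.* SAP 6.2.1 lists "Change from Baseline in BMI over time" among the metabolic endpoints. Its baseline value is already the covariate.
- *Absolute weight change.* Assume a between-person coefficient of variation c of 15% to 25%, and take s = 4.6 or 4.0 from SAP 1.5. Then r ≈ 1 − s²/(2c²) runs from 1 − 21.16/450 = 0.953 to 1 − 16/1250 = 0.987. The gain (1 − r)/2 is 2.4% to 0.6% before any credit for BMI, and less with BMI in the model.
- *Primary percent weight change.* If baseline weight has partial correlation 0, 0.1, 0.2 or 0.3 with the outcome given BMI, sex and race, residual variance is multiplied by 1.00, 0.99, 0.96 or 0.91, and power goes from 0.801 to 0.801, 0.805, 0.817 or 0.837. The low end is the plausible one. In a simulation with assumed anthropometry (BMI mean 31, SD 6; height SD 7 cm within sex; 70% male), BMI and sex explained about 85% of the variance in baseline weight, and adding baseline weight cut residual variance by 0 to 0.3%.

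**Can the primary model simply be copied?** The Schedule of Activities places DEXA, the fasting metabolic profile, leptin and adiponectin at Baseline, Week 24 and Week 48 (and at early discontinuation). Up to Week 24 that is one scheduled post-baseline value per participant, so a random subject effect cannot be separated from residual error. Blood pressure and waist circumference are also measured at Weeks 4 and 12, so a repeated-measures model is available for them.

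**The case against.** The strongest reply is that the SAP governs. Protocol section 9 calls itself a general description and leaves specifics to the SAP, which is also the later document (24 March 2023 against 29 April 2022). If SAP 6.2.2.1 stands, no secondary metabolic endpoint is modelled, and there is no model to which a covariate could be added. This stands as far as it goes: reuse of the primary model is protocol text only. But raw mean changes do not use the endpoint's own baseline either, the objectives remain comparative, and the conflict between the two sections has to be resolved in any case.

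The second reply is that the variance figures are generous. They compare with a wholly unadjusted change score, and BMI is an obvious partial proxy for DEXA composition. This stands. The figures are upper values at each assumed correlation.

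The third concerns the primary model. The final test combines p-values from the interim and later stages, and the SAP amendment history cites feedback from interim outputs as a reason for one change. Altering the primary covariates after an unblinded interim in an open-label trial would raise a pre-specification question for a gain probably under 1%. This stands in full.

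**Conclusion.** The point holds for the secondary metabolic change endpoints other than weight and BMI, as a minor matter of efficiency together with an inconsistency between the documents. The loss is about 25% to 5% of residual variance for correlations of 0.5 to 0.9. This rests on assumed correlations, equal variances and no explanatory role for BMI; the loss is smaller where BMI stands in for part of the baseline.

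Three stronger readings are tempting, and the documents do not support them.

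- A reader might infer that the primary analysis loses useful precision by leaving out baseline weight. The outcome is already expressed relative to baseline weight, and BMI with sex carries most of what remains, so the gain is probably negligible.
- A reader might infer that the trial is undersized. The sample size covers only the primary endpoint and assumes an unadjusted t-test; 55 per arm and 80% power are unaffected.
- A reader might infer that the estimates are biased. Randomization keeps them unbiased on average. What remains is dependence on the imbalance that happens to occur.

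**What to change.** Reconcile Protocol 9.4.3.1 with SAP 6.2.2.1 by stating in both that the between-arm Week 24 difference will be estimated for change in blood pressure, lipids, glucose, HOMA-IR, HbA1c, leptin, adiponectin, waist circumference and DEXA measures. Use a model containing the endpoint's own baseline value, sex and race:

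- ANCOVA where Week 24 is the only scheduled post-baseline value up to that point;
- the repeated-measures model with a baseline-by-visit term where earlier visits exist, as for blood pressure and waist circumference.

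Change in BMI needs no added term. Leave the primary model as pre-specified; baseline weight should appear at most in a supportive analysis, labelled as such. The descriptive summaries can stay alongside.

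The cost is a short SAP amendment and one or two model terms per endpoint. No new data are needed, and neither the sample size nor the primary test changes.
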